## 1.2 Schema

## 1.3 Schedule of activities

### 1.3.1 Schedule of activities, nanrilkefusp alfa combined with pembrolizumab

Cycle	Visit	Cycle 1 and cycle 2						From cycle 3 onwards				End of treatment  Within 7 (+7) days after the last dose of nanrilkefusp alfa and/or pembrolizumab (whichever occurs later)	Follow-up	
		Screening Up to 28 days before day 1 of cycle 1	Day 1	Day 2	Day 6	Day 8	Day 9	Day 13	Day 1	Day 2	Day 8	Day 9		
Informed consent 		X												
Demography 		X												
Cancer  and medical history		X												
Height		X												
Pregnancy test		X (blood)	X (urine or blood) 						X (urine or blood) 				X (urine or blood) 	
Physical examination		X	X 	X 	X	X 	X 	X	X 	X 	X 	X 	X	X 
Body weight		X	X 						X 				X	
Vital signs		X	X 	X 	X	X 	X 	X	X 	X 	X 	X 	X	X 
Urinalysis 		X	X 			X 			X 		X 		X	
Electrocardiography		X	X 						X 				X	
Left ventricular ejection fraction 		X	End of each second cycle (i.e., cycle 2, 4, 6...; allowed interval from day 9 of the current cycle to day 2 of the next cycle)									X		
Eastern Cooperative Oncology Group performance score		X	X 						X 				X	X 
Tumor assessment (CT/MRI/bone scan)		X 	Every 6 weeks ( $\pm$ 2 weeks) starting from day 1 of cycle 1 until disease progression identified by the investigator, start of a new anti-cancer treatment, pregnancy of the patient, withdrawal of consent by the patient, or end of the study											
Nanrilkefusp alfa administration 			X	X	X	X			X	X	X	X		
Pembrolizumab administration 			Every 3 weeks (day 1) according to the prescribing information											
Tumor biopsy 		X	X											
Adverse events		X	X											X 
Concomitant medication/ non-drug therapies		X	X											X 
Survival information														X 

---

1. Criteria for discontinuation of study interventions are listed in section 7.1. In case nanrilkefusp alfa needs to be discontinued for reasons other than disease progression, pembrolizumab treatment can continue for up to a total of 35 administrations (approximately 2 years) in patients without disease progression or unacceptable toxicity. A schedule of activities for patients who continue pembrolizumab after discontinuation of nanrilkefusp alfa is shown in section 1.3.2. In case pembrolizumab needs to be discontinued, nanrilkefusp alfa treatment can continue until disease progression or unacceptable toxicity and the schedule of activities for patients receiving nanrilkefusp alfa combined with pembrolizumab will apply (not applicable in the Czech Republic). In the Czech Republic: In case pembrolizumab needs to be discontinued, nanrilkefusp alfa treatment will be discontinued as well.
2. No study-specific procedures are to be performed before ICF signature.
3. Age at screening and gender
4. Primary tumor location, histology/cytology, initial diagnosis date, lines of previous treatment, start and stop dates of the treatments before this study, any prior mutations/genetic analysis (e.g., EGFR, ALK mutations), and the date of the latest disease progression if not coinciding with the stop date
5. Before nanrilkefusp alfa administration
6. Every 30 ( $\pm 2$ ) days until 120 ( $\pm 2$ ) days after the last dose of pembrolizumab or 30 ( $\pm 2$ ) days after the last dose of nanrilkefusp alfa, whichever is later
7. Before nanrilkefusp alfa administration and afterwards as clinically required
8. Follow-up visits 30 ( $\pm 2$ ) days and 90 ( $\pm 2$ ) days after the last dose of nanrilkefusp alfa and/or pembrolizumab (whichever occurs later)
9. Before and after nanrilkefusp alfa administration as described in section 8.2.3
10. In case of proteinuria  $\geq 100$  mg/dL at screening, a 24-hour urine analysis will have to be performed (before the start of nanrilkefusp alfa treatment) to document 24-hour proteinuria levels and a urine test will continue during the treatment period. In case of increase of proteinuria with  $\geq 300$  mg/dL (at any time), a 24-hour urine analysis will be performed.
11. Using either echocardiography or MUGA; the method chosen needs to stay the same throughout the trial
12. Tumor scans performed as part of routine clinical management are acceptable for screening if they are of acceptable diagnostic quality and performed within 28 days of day 1 of cycle 1.
13. Time to be recorded
14. Time to be recorded; pembrolizumab will be administered within 30 minutes following nanrilkefusp alfa administration
15. A fresh biopsy must be taken during screening unless the biopsy cannot be obtained due to safety reasons or non-accessibility of the tumor site. If it is not possible to obtain a fresh biopsy, every effort should be taken to retrieve an archival biopsy. Archived, fixed tumor tissue may only be collected if taken preferentially after completion of the most recent systemic tumor therapy and within 12 months prior to the first dose of study treatment. Investigators are highly encouraged to obtain an optional biopsy at cycle 2 day 13 and at disease progression or at any other clinically relevant event if it does not expose the patient to an increased risk.
16. Contacts every 3 months ( $\pm 2$  weeks) during year 1 and then every 6 months ( $\pm 2$  weeks) until the end of the study

ALK, anaplastic lymphoma kinase; CT, computed tomography; EGFR, epidermal growth factor receptor; ICF, Informed Consent Form; MRI, magnetic resonance imaging; MUGA, multigated acquisition scanning

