### 1.3.3 Collection of blood samples, nanrilkefusp alfa combined with pembrolizumab

All attempts should be made to collect the samples on time.

Cycle	Screening	Cycle 1						Cycle 2					Cycle 3				From cycle 4				End of treatment
		1	2	6	8	9	13	1	2	6	8	9	1	2	8	9	1	2	8	9	
Nanrilkefusp alfa administration 		X	X		X	X		X	X		X	X	X	X	X	X	X	X	X	X	
Pembrolizumab administration 		X						X					X				X				
Serum for nanrilkefusp alfa PK													See section 1.3.5								
Serum for cytokines 		X	X		X	X		X	X		X	X									
Serum for nanrilkefusp alfa immunogenicity 		X						X									Cycle 4 only				X
Serum for pembrolizumab PK 		X						X									Cycles 4 and 8 only				X
Serum for pembrolizumab immunogenicity 		X						X									Cycle 4 only				X
Whole blood for RNA and DNA analysis 		X		X				X		X											
HIV, HBV, and HCV	X																				
Hematology (full complete blood count including absolute lymphocyte count)	X	X 	X 	X	X 	X 	X	X 		X	X 		X 		X 		X 		X 		X
Biochemistry (including C-reactive protein)	X	X 	X 	X		X 	X	X 		X		X 	X 		X 		X 		X 		X
Creatinine clearance	X	X 		X		X 		X 		X		X 	X 		X 		X 		X 		
C-reactive protein				X 					X 		X 										
Coagulation	X	X 		X 				X 		X 			X 		X 		X 		X 		X
TSH, T3 or free T3, free T4	X	X 											X 				X 				X
Patients with mCRPC: PSA, alkaline phosphatase, lactate dehydrogenase, CTCs, circulating tumor DNA fraction	X		X 										X 				X 				
Serum pregnancy	X																				

1. Time to be recorded
2. Time to be recorded; pembrolizumab will be administered within 30 minutes following nanrilkefusp alfa administration.
3. Before nanrilkefusp alfa administration and 4 hours ( $\pm 30$  min) after nanrilkefusp alfa administration
4. Within 1 day before nanrilkefusp alfa administration

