### **8.3.1.3 Adverse events of special interest**

The following AEs are defined for this Protocol as AESIs and must be reported to the sponsor or designee within 24 hours of awareness:

1. For patients without liver metastases or liver cancer or patients who do not receive hepatotoxic concomitant medications, the following AESIs must be reported:
  - a. On-treatment (i.e., from the first dose of study treatment to 90 days after the last dose of study treatment) ALT or AST increase that is greater than  $3\times$ ULN in combination with clinical jaundice
  - b. On-treatment ALT increase that is greater than or equal to  $3\times$ ULN and international normalized ratio increase that is greater than 1.5
  - c. Recurrence of CTCAE grade 3 ALT and/or AST increase in combination with total bilirubin increase greater than  $2\times$ ULN or greater than  $2\times$ baseline level
2. For patients with liver metastases or liver cancer or patients who receive hepatotoxic concomitant medications, the following AESIs must be reported:
  - a. On-treatment ALT or AST increase that is greater than  $5\times$ ULN in combination with total bilirubin increase greater than  $2\times$ ULN (of which more than or equal to 35% is direct bilirubin)

---

- b. On-treatment ALT or AST increase that is greater than  $5\times\text{ULN}$  in combination with clinical jaundice
- 3. An overdose of pembrolizumab, as defined in section [6.7](#)
- 4. An elevated AST or ALT laboratory value that is greater than or equal to  $3\times\text{ULN}$  and an elevated total bilirubin laboratory value that is greater than or equal to  $2\times\text{ULN}$  and, at the same time, an alkaline phosphatase laboratory value that is less than  $2\times\text{ULN}$ , as determined by way of Protocol-specified laboratory testing or unscheduled laboratory testing\*

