#### **8.3.2 Time period and frequency for collecting AE, SAE, and other reportable safety event information**

Every effort should be taken to collect all AEs, AESIs, and SAEs from the date of the patient’s signing the ICF until 90 days after the final administration of nanrilkefusp alfa and/or pembrolizumab (whichever is later) or until the start of a new anti-cancer therapy, whichever is earlier.

---

Additionally, any SAE brought to the attention of an investigator at any time outside of the time period specified above must be reported immediately to the sponsor or designee if the event is considered as having a suspected causal relationship to nanrilkefusp alfa and/or pembrolizumab per the investigator's judgment.

Pregnancies of the patient or patient's female partner must be reported from the date of the patient's signing the ICF up to 120 days following the last dose of pembrolizumab or 30 days after the last dose of nanrilkefusp alfa, whichever is later.

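### SAP 10.15.2 keeps one of the protocol's six hepatic AESI criteria and rules out other liver test abnormalities, and SAP 6.1 does not declare the change

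*Protocol*

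**What the plan says.** **Protocol, definition (8.3.1.3).** Items 1a to 1c apply to patients without liver metastases or liver cancer, or not on hepatotoxic co-medication. Items 2a and 2b apply to patients with any of these. Item 3 is pembrolizumab overdose. Item 4 is the Hy's-law-type combination, "as determined by way of Protocol-specified laboratory testing or unscheduled laboratory testing". Item 1a fixes the time frame of the hepatic items: "On-treatment (i.e., from the first dose of study treatment to 90 days after the last dose of study treatment) ALT or AST increase". Item 1c is "Recurrence of CTCAE grade 3 ALT and/or AST increase in combination with total bilirubin increase greater than" 2×ULN or 2×baseline. A closing note says that liver abnormalities not meeting the criteria are not AESIs. There, the note follows all six hepatic criteria.

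**Protocol, collection (8.3.2).** "Every effort should be taken to collect all AEs, AESIs, and SAEs" from consent until 90 days after the last dose, "or until the start of a new anti-cancer therapy, whichever is earlier".

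**Protocol, schedule.** End of treatment is "Within 7 (+7) days after the last dose of nanrilkefusp alfa and/or pembrolizumab (whichever occurs later"), so day 14 at the latest. In 1.3.3 the row "Biochemistry (including C-reactive protein") and the coagulation row both stop at End of treatment, and 1.3.4 does the same. Footnote 8 of 1.3.1 sets follow-up visits at 30 (±2) and 90 (±2) "days after the last dose of nanrilkefusp alfa and/or pembrolizumab (whichever occurs later"). In 1.3.1 and 1.3.2, the day-30 and day-90 visits cover physical examination, vital signs, ECOG, adverse events and concomitant medication. Pregnancy tests run separately.

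**SAP.** Sections 4.0 and 6.0 tie the SAP to Amendment 1 of 20 April 2023 and to CRF version 1.0 of 28 February 2022. Section 10.15.2 says AESIs come from the AE CRF page. It then lists two items, pembrolizumab overdose and protocol item 4, and repeats the closing note. Section 6.1 (changes from protocol) does not mention AESIs. Section 12.8.1.1 uses AESIs in one summary by SOC and PT and in one listing.

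**The concern.** The closing note does different work in the two documents. Under the protocol's long list it only excludes abnormalities that meet none of six criteria. Under the SAP's short list the same sentence excludes events that the protocol defines as AESIs and requires sites to report within 24 hours. Both criteria written specifically for patients with liver metastases or liver cancer (2a and 2b) are absent, and the trial has a hepatocellular carcinoma cohort.

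Two things are at stake. A programmer or medical reviewer who follows SAP 10.15.2 literally could drop or reclassify events that sites reported correctly. And a reader of the study report could not tell which definition lies behind the AESI counts.

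A second point concerns how those counts are read. AESIs are collected to day 90, but scheduled liver testing stops at End of treatment. After that, a new event without symptoms would come to light only through an unscheduled test. Nothing in the planned AESI output says so.

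**Working it through.** **1. Count the criteria.** Protocol 8.3.1.3: 1a, 1b, 1c, 2a, 2b, 4 = 6 hepatic criteria. SAP 10.15.2: item 4 = 1. Absent: 6 − 1 = 5.

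**2. Does item 4 cover the absent five?** Item 4 needs ALT or AST ≥3×ULN, total bilirubin ≥2×ULN and ALP <2×ULN. Comparing each absent criterion with it:

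| Criterion | Requires | Met, but outside item 4, when |
|---|---|---|
| 1a | ALT or AST >3×ULN, clinical jaundice | bilirubin <2×ULN or ALP ≥2×ULN |
| 1b | ALT ≥3×ULN, INR >1.5 | bilirubin <2×ULN or ALP ≥2×ULN |
| 1c | recurrent grade 3 ALT/AST, bilirubin >2×ULN or >2×baseline | ALP ≥2×ULN, or bilirubin >2×baseline but <2×ULN |
| 2a | ALT or AST >5×ULN, bilirubin >2×ULN with at least 35% direct | ALP ≥2×ULN |
| 2b | ALT or AST >5×ULN, clinical jaundice | bilirubin <2×ULN or ALP ≥2×ULN |

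Each of the five can therefore be met without item 4. They also overlap with item 4, so the SAP wording loses part of each category, not the whole of it.

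**3. Do other SAP outputs recover these events?**
- The Hy's-law table (12.8.2.2) uses the item 4 thresholds and is limited to the SAP on-treatment period. Section 10.6 ends that period no later than the day before the End of treatment visit.
- The eDISH figure and the at-risk listing are not limited to that period. As worded, the figure has no ALP condition, so it would show 1c or 2a events that miss item 4 on ALP alone. It would not show a 1b event with bilirubin below 2×ULN.
- INR is not summarized: 12.8.2.1 selects only D-dimer from the coagulation tests. Outside the AESI output, such a 1b event would be visible only in data listings.

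**4. Time without a scheduled liver test.** The plan states no figure to reproduce. Days without a test = T − E, where E is the day of End of treatment and T the end of collection, both counted from the last dose.
- T = 90, E = 14 (latest allowed): 90 − 14 = 76 days; 76/90 = 84.4%.
- T = 90, E = 7: 83 days; 83/90 = 92.2%.
- New therapy ends collection earlier (assumed dates, E = 14): T = 60 gives 46 days (76.7%), T = 30 gives 16 (53.3%), T = 21 gives 7 (33.3%).

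These are shares of calendar time. The documents give no rate, onset or duration for late liver events, so no number of missed events follows.

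**5. What tests at days 30 and 90 would change.** The longest stretch without a scheduled test becomes 90 − 30 = 60 days. With the ±2-day windows, and counting stopped at day 90, it runs from 88 − 32 = 56 to 90 − 28 = 62 days. The gap narrows but does not close.

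**The case against.** **On the definition.** SAP 10.15.2 opens by taking AESIs from the AE CRF page, and SAP 6.0 says the SAP is read with the protocol. AESI status then follows what the site recorded under protocol 8.3.1.3, not a program run on the two-item list. This stands, and it limits the likely effect. A reader might infer that 1b or 2a events will drop out of the AESI table. The documents do not show that. But the argument leaves the SAP with a stated rule that contradicts its own data source, and no text says which prevails.

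**On the testing gap.** The trial is single-arm and descriptive, and no planned analysis compares liver events before and after End of treatment. Unscheduled tests count under item 4. Examination and AE questioning can find symptomatic events. Known AESIs are followed to resolution or stabilization (8.3.4). Criterion 1c requires a recurrence, so that patient already has a known liver event. Collection often may not run to day 90, because new therapy ends it. The AESI listing and the defined study day should let a reader see late onset. All of this stands. A reader might infer that the schedule contradicts the 90-day window, or that 84% of late liver events would be missed. Neither follows: the protocol does not promise scheduled tests through day 90, and 84% describes days, not events. Protocol 6.5.2.1 says immune-related events can appear months after the last dose, but that is a general warning and gives no frequency for liver events.

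**Conclusion.** The SAP's AESI definition does not match the protocol it is written to. Five of six hepatic criteria are absent, other liver abnormalities are expressly ruled out, and SAP 6.1 declares nothing. This is a documentation error that should be corrected. Its effect on the reported counts is probably small, because identification runs through the AE CRF page, but it cannot be sized: the documents give no event counts and do not say whether the CRF records which criterion was met.

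The testing gap is a matter of interpretation, not an error in the schedule. The minimum of 76 days assumes that End of treatment is held within its window, that the patient starts no new anti-cancer therapy before day 90, and that no unscheduled test is done. It justifies a caveat on the AESI output. It does not make liver tests at days 30 and 90 a required correction.

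**What to change.** 1. **SAP 10.15.2.** Replace the two-item list with the full list in protocol 8.3.1.3, and keep identification from the AE CRF page. Carry over the protocol's definition of on-treatment for these items (first dose to 90 days after the last dose). Otherwise the shorter period in SAP 10.6 could be applied to them.
2. **SAP 12.8.1.1.** Use that list for the AESI table and listing.
3. **Footnote to both.** Suggested content: *No liver tests were scheduled after End of treatment (at least 76 of 90 days for a patient followed throughout); a low number of late hepatic AESIs is not evidence that late liver toxicity is absent.* A split of the table at End of treatment is presentational and not needed.

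**Cost.** A SAP update, with no protocol amendment and no new data collection. If the CRF does not record the criterion met, a small amount of programming or medical review is needed, because items 1 and 2 depend on liver metastases or liver cancer, hepatotoxic co-medication and, for 1a and 2b, clinical jaundice.

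**Optional, for the sponsor.** ALT, AST, total and direct bilirubin, ALP and INR could be added at the existing day-30 and day-90 visits for patients not on new anti-cancer therapy. That costs two blood samples per patient, work-up of some abnormalities due to progression, and an amendment resubmitted under protocol 10.1.1. It would still leave a stretch of about 60 days. Recruitment stopped after the August 2023 futility analysis (SAP 6.1), so few patients may benefit; the number is not stated. If it is adopted, the footnote should say which patients had the tests.

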### 1.3.2 Schedule of activities, for patients who continue pembrolizumab after discontinuation of nanrilkefusp alfa

Visit	Day 1 of each cycle	End of treatment	Follow-up
Pregnancy test	X (urine or blood) 	Within 7 (+7) days after the last dose of pembrolizumab	X (urine or blood) 
Physical examination	X 	X	X 
Body weight	X 	X	
Vital signs	X 	X	X 
Urinalysis 	X 	X	
Electrocardiography	X 	X	
Left ventricular ejection fraction 		X	
Eastern Cooperative Oncology Group performance score	X 	X	X 
Tumor assessment (CT/MRI/bone scan)	Every 6 weeks ( $\pm 2$ weeks) starting from day 1 of cycle 1 until disease progression identified by the investigator, start of a new anti-cancer treatment, pregnancy of the patient, withdrawal of consent by the patient, or end of the study		
Pembrolizumab administration	Every 3 weeks (day 1) according to the prescribing information		
Adverse events	X		X 
Concomitant medication/non-drug therapies	X		X 
Survival information			X 

1. Before pembrolizumab administration
2. Every 30 ( $\pm 2$ ) days until 120 ( $\pm 2$ ) days after the last dose of pembrolizumab
3. Follow-up visits 30 ( $\pm 2$ ) days and 90 ( $\pm 2$ ) days after the last dose of pembrolizumab
4. In case of proteinuria  $\geq 100$  mg/dL at screening, a 24-hour urine analysis will have to be performed (before the start of nanrilkefusp alfa treatment) to document 24-hour proteinuria levels and a urine test will continue during the treatment period. In case of increase of proteinuria with  $\geq 300$  mg/dL (at any time), a 24-hour urine analysis will be performed.
5. Using either echocardiography or MUGA; the method chosen needs to stay the same throughout the trial
6. Contacts every 3 months ( $\pm 2$  weeks) during year 1 and then every 6 months ( $\pm 2$  weeks) until the end of the study

CT, computed tomography; MRI, magnetic resonance imaging; MUGA, multigated acquisition scanning

### 1.3.3 Collection of blood samples, nanrilkefusp alfa combined with pembrolizumab

All attempts should be made to collect the samples on time.

Cycle	Screening	Cycle 1						Cycle 2					Cycle 3				From cycle 4				End of treatment
		1	2	6	8	9	13	1	2	6	8	9	1	2	8	9	1	2	8	9	
Nanrilkefusp alfa administration 		X	X		X	X		X	X		X	X	X	X	X	X	X	X	X	X	
Pembrolizumab administration 		X						X					X				X				
Serum for nanrilkefusp alfa PK													See section 1.3.5								
Serum for cytokines 		X	X		X	X		X	X		X	X									
Serum for nanrilkefusp alfa immunogenicity 		X						X									Cycle 4 only				X
Serum for pembrolizumab PK 		X						X									Cycles 4 and 8 only				X
Serum for pembrolizumab immunogenicity 		X						X									Cycle 4 only				X
Whole blood for RNA and DNA analysis 		X		X				X		X											
HIV, HBV, and HCV	X																				
Hematology (full complete blood count including absolute lymphocyte count)	X	X 	X 	X	X 	X 	X	X 		X	X 		X 		X 		X 		X 		X
Biochemistry (including C-reactive protein)	X	X 	X 	X		X 	X	X 		X		X 	X 		X 		X 		X 		X
Creatinine clearance	X	X 		X		X 		X 		X		X 	X 		X 		X 		X 		
C-reactive protein				X 					X 		X 										
Coagulation	X	X 		X 				X 		X 			X 		X 		X 		X 		X
TSH, T3 or free T3, free T4	X	X 											X 				X 				X
Patients with mCRPC: PSA, alkaline phosphatase, lactate dehydrogenase, CTCs, circulating tumor DNA fraction	X		X 										X 				X 				
Serum pregnancy	X																				

1. Time to be recorded
2. Time to be recorded; pembrolizumab will be administered within 30 minutes following nanrilkefusp alfa administration.
3. Before nanrilkefusp alfa administration and 4 hours ( $\pm 30$  min) after nanrilkefusp alfa administration
4. Within 1 day before nanrilkefusp alfa administration
5. Up to 24 hours before pembrolizumab infusion at cycles 1, 2, 4, and 8; within 30 minutes of the end of pembrolizumab infusion at cycles 1, 2, and 8; and at the End of treatment visit; sampling times to be recorded
6. Up to 24 hours before pembrolizumab infusion at cycles 1, 2, and 4; and at the End of treatment visit; sampling times to be recorded
7. Samples for RNA analysis: day 1 (before nanrilkefusp alfa administration) and day 6 of cycles 1 and 2; samples for DNA analysis: day 1 (before nanrilkefusp alfa administration) of cycle 1 only
8. On the day of dosing before nanrilkefusp alfa administration
9. Every other cycle

CTC, circulating tumor cell; HBV, hepatitis B; HCV, hepatitis C; mCRPC, metastatic castration-resistant prostate cancer; PK, pharmacokinetics; PSA, prostate-specific antigen; T3, triiodothyronine; T4, thyroxine; TSH, thyroid stimulating hormone

